#### 9.3 Primary Efficacy Endpoint and Analyses

#### 9.3.1 Primary Efficacy Endpoint

The primary efficacy endpoint is the status of each live female adult worm as without *Wolbachia*, assessed by immunohistology of nodules collected after nodulectomy at Month 6.

#### 9.3.2 Main Analysis of Primary Efficacy Endpoint

The primary efficacy endpoint will be compared between the following pairs of treatment arms for the PP population in Part 1:

- For proof of concept: (1) A vs. E, (2) B vs. E, (3) C vs. E, (4) D vs. E;
- For satisfying the combination rule: if Arm C is to advance to Study B18-894/DNDi-TYL-01 Part 2, then (1) C vs. A, (2) C vs. E; if Arm D is to advance to Part 2 but Arm C is not, then: (1) D vs. A, (2) D vs. E.

The comparisons will be conducted using contrasts from an alternating logistic regression model that includes all the five treatment arms as factors. The alternating logistic regression will account for within-subject association of the worm-level endpoint by estimating the pairwise log odds ratio (different than the odds ratio of the primary estimand) of a worm's Wolbachia status in relation to another worm's Wolbachia status within each subject. In this regression model, the within-subject association is estimated with one parameter. That is, the pairwise log odds ratios used to account for the within-subject association are assumed as equal for all pairs of worms within a subject, and the same log odds ratios are assumed for all subjects in the same treatment arm. However, different log odds ratios/parameters are assumed in different treatment arms, allowing for arm-specific within-subject associations. If the model does not converge, the within-subject associations for the five treatment arms will be assumed as the same. If the model still does not converge, a generalized linear mixed model will be used instead of the alternating logistic regression model. The mixed model will assume the framework of a logistic regression using a random intercept for each subject to account for the within-subject association of the worm-level endpoint. The variance of the random intercepts will be assumed as different for the five treatment arms.

Odds ratios with p-values and 95% confidence intervals for each of the pairwise comparisons will be reported. In addition, the percentages of live female adult worms without *Wolbachia* out of all live female adult worms from subjects in the PP population will also be summarized by treatment arm with 95% Wilson's score confidence intervals for all the percentages. The numerator and denominator of the percentage will be a sum across all subjects in a treatment arm. The rules of Section 9.2 for imputing missing data in the PP population worms will be applied; any worms that still have missing *Wolbachia* status after that will be excluded from both the numerator and denominator.

The attributes of the estimands corresponding to the primary efficacy endpoint are summarized in Table 1.

		A	Attributes of the	e Estimand	
Estimand Label	Treatment	Endpoint	Population	Handling of Intercurrent Events	Statistical Summary
Proof of concept	Arm A: ABBV-4083 for 7 days Arm B: ABBV-4083 for 14 days Arm C: ABBV-4083 for 7 days + albendazole for 7 days Arm D: ABBV-4083 for 7 days + albendazole for 3 days Arm E: albendazole for 7 days	Status of depletion of Wolbachia in each live female adult worm, evaluated using nodules collected at Month 6	PP population: all subjects who completed treatment and did not take prohibited medication, who had Month 6 nodulectomy with female worms	IE1: Subjects who did not complete treatment (6 out of 7 days for Arms A, C, E, 12 out of 14 days for Arm B, 6 out of 7 days of ABBV-4083 and all 3 days of albendazole for Arm D) will be excluded. IE2: Subjects who did not have Month 6 nodulectomy data will be excluded. IE3: Subjects who took prohibited medications will be excluded.	Odds ratio of Wolbachia depletion in live female adult worms in subjects taking active regimen vs. control regimen
Satisfying the combination rule	Arm A Arm C (or D depending on Part 2 regimens) Arm E	Same as above	Same as above	Same as above	Odds ratio of Wolbachia depletion in live female adult worms in subjects taking the combination regimen vs. the single drug regimens

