2.4 Design and Rationale for Study

2.4.1 Overview of Study Design

This phase-II study in subjects with onchocerciasis will be an adaptive study with two parts. In Part 1 (proof-of-concept [PoC]), four regimens of ABBV-4083 ± albendazole will be assessed in comparison to albendazole alone with the aim of selecting two regimens having optimal activity and safety to continue into Part 2 Regimen Selection. Part 1 will end at 6 months follow-up, and the study will be paused to evaluate nodules to determine whether the ABBV-4083 + albendazole combinations are superior to both ABBV-4083 and albendazole alone, and to select the optimal arms to continue into Part 2 (see Figure 1, Figure 2 and Figure 3). Based on earlier studies, albendazole alone is not expected to affect *Wolbachia* levels¹⁸ or to substantially interfere with embryogenesis in female worms.⁴⁴ The albendazole arm is therefore considered largely equivalent to an untreated control arm for efficacy. Selection of the regimens

for Part 2 will take into consideration the balance of efficacy, i.e. analysis of *Wolbachia* depletion in adult worms as surrogate marker, supported by effects on embryogenesis in female worms, as well as safety and convenience, i.e. the number and duration of drugs taken. The target efficacy for Part 1 will be based on comparison to studies using doxycycline, which produces $\geq 90\%$ *Wolbachia* depletion at 6 months. ^{18,45} This level of *Wolbachia* depletion at Month 6 has been correlated with the absence of skin mf at longer-term time-points. ⁴⁵

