7.3 IMP Assignment and Administration

7.3.1 IMP Assignment and Administration in Part 1

7.3.1.1 IMP Assignment in Part 1

In Part 1, the IMP will be randomly assigned. A total of 150 subjects will be recruited and centrally and continuously randomised under double blind 1:1:1:1:1 into one of five parallel groups (Arms A, B, C, D and E), based on dosing regimen, until group size is achieved. Subjects

will be stratified by the number of operable sites with onchocercomata. There will be two strata, i.e. one site and more than one site.

7.3.1.2 IMP Administration in Part 1

The IMP ABBV-4083 will be administered as 100-mg capsules or matching placebo capsules. The IMP albendazole will be administered as over-encapsulated 400-mg tablets or matching over-encapsulated placebo .

Subjects will receive a maximum of 5 capsules per day for 14 days. Depending on the treatment arm allocation, subjects will receive four ABBV-4083 capsules (400 mg) or matching placebo + one over-encapsulated albendazole tablet (400 mg) or matching placebo, once a day, from Day 0 to Day 6, followed by four ABBV-4083 capsules (400 mg) or matching placebo, once a day, from Day 7 to Day 13.

The IMPs will be administered once daily by the oral route and are to be taken with food (see Section 9.2.8 for details).

The IMP will be administered at the investigational centre at approximately the same time each morning, and intake of the IMP will be directly observed by the study personnel.

7.3.2 IMP Assignment and Administration in Part 2

7.3.2.1 IMP Assignment in Part 2

In Part 2, there will be four treatment arms. The two study arms of the shortest treatment duration in Part 1 that are likely to demonstrate high efficacy at Month 24 (based on Part 1 efficacy results and historical studies with doxycycline) and safety will be selected as active arms for Part 2. In order also to assess an additional effect of a dose of ivermectin at Month 6, participants will be into four groups stratified by the number of operable sites with onchocercomata (one site, > 1 site) and by mean skin mf (≤ 5 mf/mg, > 5 mf/mg) at Screening, with two arms receiving the same ABBV-4083 or ABBV-4083 + albendazole regimen but one receiving ivermectin at Month 6 and the other receiving ivermectin matching placebo.

In the Base Scenario, subjects will be randomly assigned 2:2:2:1 under double blind to Arms K, L, M and N1.

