10.7 Multiplicity Adjustment

Since Part 1 is a Phase-II proof-of-concept study, no adjustment will be made for the multiple comparisons in the primary endpoint (Arm A vs Arm E, Arm B vs Arm E, Arm C vs Arm A, Arm C vs Arm E, Arm D vs Arm A and Arm D vs Arm E). Each comparison will be controlled at 2-sided $\alpha = 0.10$.

In Part 2, the multiplicity adjustment to control the overall Type I error rate at 5% will include: (1) Bonferroni allocation of $\alpha = 0.017$ to each primary endpoint comparison: Arm K vs Arm N1, Arm L vs Arm N1, and Arm M vs N1; (2) a graphical approach to multiplicity adjustment to control the family-wise error at 0.05 (see Figure 6). The same method will be used in the Part 2 Alternate Scenario, with comparisons between Arms K-M and Arm N2.

[figure not shown]

Figure 6. Graphical Approach to Multiplicity Control in Part 2

Of note, the parallel graphical approach above shows how the α is passed to the next comparison if the null hypothesis is rejected.⁸¹

In the Alternate Scenario of Part 2, the primary endpoint for satisfying the combination rule in Part 1 continued in Part 2 (combination rule endpoint) is conducted at 2-sided $\alpha = 0.10$ with no need to adjust for multiplicity per Section 5.5.2 of the European Medicines Agency Guideline on Multiplicity Issues for Clinical Trials.⁸²

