10.8 Statistical Analysis of Safety

All safety analyses will be performed on the Safety Population, which consists of all subjects who received at least one dose of IMP. Safety will be assessed by AEs, laboratory tests, vital signs, and ECG variables. Details of the analyses will be provided in the Statistical Analysis Plan.

AEs will be coded using the Medical Dictionary for Regulatory Activities (MedDRA). A TEAE is defined as an AE with an onset date that is after the first intake of IMP and no more than 30 days after the last intake of IMP. The number and percentage of subjects experiencing TEAEs will be tabulated using MedDRA system-organ class and preferred term, as well as by severity and by relationship to the IMP as assessed by the Investigator. Summaries of SAEs, deaths, AEs leading to discontinuation will also be provided.

For laboratory test and vital signs variables, mean change from baseline and percentage of subjects with on-treatment laboratory values of CTCAE 5.0 adapted scale grade 3 or 4 will be summarised.

10.9 Interim Analysis of Part 1 and DSMB Recommendation to Proceed to Part 2

Once subjects in Part 1 have completed or prematurely discontinued the study, up to and including nodulectomy at 6 months, a database lock for Part 1 database and an interim analysis of data from Part 1 will be conducted by the Sponsor and the randomisation code unblinded. The unblinded data will be reviewed by the Sponsor and the DSMB (see Section 13.3), for futility and risk/benefit ratio. Taking into account the recommendations of the DSMB, especially regarding the safety assessment of the data, the Sponsor will decide whether or not to proceed to Part 2, and with which dose regimens.

Selection of up to two acceptable/suitable doses / regimens for Part 2 will be based on analysis of all of available unblinded data from Part 1, including safety and tolerability of ABBV-4083 and ABBV-4083 + albendazole, *Wolbachia* depletion, disruption of embryogenesis and an exploratory surrogate marker, microfilaria *Wolbachia*, observed at Months 3 and 6.

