# 1.0 Introduction

This Statistical Analysis Plan (SAP) describes the statistical analyses of Part 1 only for ABBV-4083 Study B18-894/DNDi-TYL-01 "A Phase-II, Randomised, Double-blind, Parallel-group, Proof-of-concept Trial to investigate ABBV-4083 given for 7 or 14 Days or in combination with Albendazole in Subjects with *Onchocerca volvulus* Infection." Part 2 will have a separate clinical database with a separate SAP and database lock.

Part 1 of Study B18-894/DNDi-TYL-01 investigates the safety, tolerability, efficacy for duration-ranging and pharmacokinetics of ABBV-4083 with or without albendazole in subjects infected with *Onchocerca volvulus*.

The analyses of pharmacokinetic endpoints and their relationship to efficacy and safety endpoints will not be covered in this SAP.

The SAP will not be updated in case of administrative changes or amendments to the protocol unless the changes impact the analysis.

Unless noted otherwise, all analyses will be performed using SAS Version 9.4 (SAS Institute Inc., Cary, NC 27513) or later under the UNIX operating system.

All analyses in this SAP are consistent with what is described in the study protocol unless otherwise noted in Section 13.0.

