#### 9.4.2 Supportive Secondary Efficacy Endpoints and Analyses

The supportive secondary efficacy endpoints include the following:

- Proportion of live female adult worms with only degenerated embryos out of all live female adult worms with either normal embryos or only degenerated embryos in the uterus per subject at Month 6;
- Proportion of live female adult worms out of all female adult worms per subject at Month 6;
- The status of each subject as without microfilariae in nodular tissue at Month 6;
- The status of each subject as without skin microfilariae at Months 3 and 6;
- The reduction in skin microfilarial density (defined as the mean number of microfilariae/mg per subject) at Months 3 and 6 compared to baseline;
- The status of each nodule that contains at least 1 live female adult worm as without *Wolbachia*, as assessed by PCR, at Month 6.

All supportive secondary efficacy endpoints will be analyzed in the ITT population using observed data. All summaries will be produced by treatment arm.

The proportion of live female adult worms out of all female adult worms in each subject at Month 6 will be calculated as a percentage per subject. The proportion of live female

adult worms with only degenerated embryos out of all live female adult worms with either normal embryos or only degenerated embryos in the uterus in each subject at Month 6 will also be calculated as a percentage per subject, excluding from the denominator any worm with an empty uterus, with oocytes only, or not evaluable. Subjects with no worm for the denominator will be excluded from this summary. The percentage per subject will be summarized with descriptive statistics (number of subjects, mean and standard deviation, median, Q1, Q3, minimum, and maximum). P-values for the pairwise comparison of each of Arms A, B, C, D with Arm E will be provided using the Mann Whitney U test for the percentage per subject.

The status of each subject as without microfilariae in nodular tissue at Month 6 will be summarized as the percentage of subjects without microfilariae in nodular tissue at Month 6. The status of each subject as without skin microfilariae or not at Months 3 and 6 will be summarized in the same way. P-values for the pairwise comparison of each of Arms A, B, C, D with Arm E will be provided using the chi-square test for the binary response per subject.

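### Part 1 is described as duration-ranging, but it plans no direct estimate of 14 v 7 days of ABBV-4083 (B v A) or 7 v 3 days of albendazole (C v D)

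*SAP*

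**What the plan says.** **Aim and selection.** SAP 1.0 says Part 1 "investigates the safety, tolerability, efficacy for duration-ranging and pharmacokinetics of ABBV-4083 with or without albendazole". Protocol 7.3.2.1 describes the active arms for Part 2 as "The two study arms of the shortest treatment duration in Part 1 that are likely to demonstrate high efficacy at Month 24". Protocol 2.4.1 also weighs safety and convenience, including how many drugs are taken and for how long, and sets a benchmark: "The target efficacy for Part 1 will be based on comparison to studies using doxycycline". Protocol 10.9 says the choice of "regimens for Part 2 will be based on analysis of all of available unblinded data from Part 1".

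**Planned contrasts.** SAP 9.3.2 gives "For proof of concept: (1) A vs. E, (2) B vs. E, (3) C vs. E, (4) D vs. E" and, for the combination rule, C v A and C v E (or D v A and D v E if only D advances). Protocol 10.7 lists "Arm A vs Arm E, Arm B vs Arm E, Arm C vs Arm A, Arm C vs Arm E, Arm D vs Arm A"; its sixth contrast is D v E, and protocol 10.5 has the same six. For the secondary endpoints that are tested, SAP 9.4.2 provides "P-values for the pairwise comparison of each of Arms A, B, C, D with Arm E".

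**Reported results.** All primary contrasts come from one alternating logistic regression with five arms. SAP 9.3.2 reports odds ratios with p-values and 95% confidence intervals, and each arm's percentage of worms without *Wolbachia* with a 95% Wilson interval on worms summed over subjects.

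**Part 2.** Protocol 10.3.2 gives power for comparing two active arms on the Month 24 primary endpoint, and 10.6 plans exploratory regimen/duration comparisons for the key secondary endpoints.

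**The concern.** All planned ABBV-4083 arms use 400 mg. The only pairs that change one drug's duration and nothing else are A and B (7 v 14 days of ABBV-4083) and C and D (7 v 3 days of albendazole). A rule that prefers shorter regimens needs to know how much depletion a shorter course gives up. That quantity is B v A or C v D, and Part 1 does not plan to report either one.

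If the sponsor wants these contrasts at selection, they will be run after the Part 1 unblinding described in protocol 10.9, without prespecification. Otherwise, regimens will be compared through two odds ratios against a third arm, or through per-arm intervals that look more precise than they are.

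**Working it through.** **1. Inputs.** From protocol 10.3.1: worms per subject 1 to 10 with probabilities 0.20, 0.16, 0.16, 0.16, 0.08, 0.08, 0.08, 0.03, 0.03, 0.02; ICC 0.54 in the 30% and 70% arms and 0.01 in the 90% combination arm; 2-sided 0.10; 30 enrolled per arm with 17% dropout, so 30 × 0.83 = 24.9, about 25 evaluable. The documents give no rates for B v A or C v D. Protocol 10.3.1 puts both A and B at 70%, so the gaps below are assumptions.

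**2. The plan's own figures.** Clustered binary outcomes were simulated (20,000 trials per case). The test was a GEE Wald test with arm-specific exchangeable correlation and robust variance, standing in for alternating logistic regression. For 17 per arm, 70% v 30%, it gives 89% (stated 88%). For 25 per arm, 90% v 70%, it gives 83–84% (stated 81%; working independence gives 81%). The stand-in is adequate but slightly liberal: with equal arms it rejects in 11.6% to 14.0% of trials against a nominal 10%, so the powers in step 6 are if anything a little high.

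**3. Significance against E.** With 25 per arm and E at 30%:
- A 70%, B 90% (plan ICCs): A v E and B v E both significant in about 97% of trials.
- A and B both 90% (ICC 0.01): both significant in about 100%.

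The pattern of p-values barely changes with the value of the second week.

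**4. Size of the odds ratios against E.** These do differ. For 70% v 30%, (0.7/0.3)/(0.3/0.7) = 5.4; for 90% v 30%, (0.9/0.1)/(0.3/0.7) = 21. The B v A point estimate is the ratio of the two, 21/5.44 = 3.86. Its confidence interval cannot be read off the two intervals against E, because both contain Arm E's variance.

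**5. Per-arm Wilson intervals.** Mean worms per subject = 3.79 and mean square = 19.99, so the design effect = 1 + (19.99/3.79 − 1) × 0.54 = 3.31. With 25 subjects there are 25 × 3.79 = 94.75 worms, worth 94.75/3.31 = 28.6 independent ones. The Wilson half-width is z√(p(1−p)/N + z²/4N²)/(1 + z²/N):
- 70%: 9.1 points with N = 94.75; 15.9 with N = 28.6.
- 90%, ICC 0.54: 6.1 v 11.3.
- 90%, ICC 0.01: 6.1 v 6.3.

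**6. What the missing contrasts would deliver** (25 per arm, power at 2-sided 0.10; the 95% limits are the estimate divided and multiplied by the factor exp(1.96 × SE)):

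| Contrast | Assumed rates (ICC) | Odds ratio | Median SE | Factor | Power |
|---|---|---|---|---|---|
| B v A | 90% (0.01) v 70% (0.54) | 3.86 | 0.504 | 2.7 | 84% |
| B v A | 90% (0.54) v 70% (0.54) | 3.86 | 0.664 | 3.7 | 70% |
| B v A | 85% (0.54) v 70% (0.54) | 2.43 | 0.597 | 3.2 | 48% |
| B v A | 80% (0.54) v 70% (0.54) | 1.71 | 0.560 | 3.0 | 28% |
| C v D | 90% (0.01) v 80% (0.54) | 2.25 | 0.548 | 2.9 | 43% |
| C v D | 90% (0.54) v 80% (0.54) | 2.25 | 0.698 | 3.9 | 35% |
| C v D | 90% (0.01) v 80% (0.01) | 2.25 | 0.429 | 2.3 | 61–62% |

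For 80% v 70%, a typical interval would run from 1.71/3.0 = 0.57 to 1.71 × 3.0 = 5.1.

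**7. Part 2.** Protocol 10.3.2 states 80% power for 90% v 70% between two active arms, 62 per arm, 2-sided 0.05; the check gives 80.3%. These comparisons come after selection, cover at most two regimens, and Arm M may differ from the other arms in ivermectin at Month 6 (protocol 3.3). Against Arm N2, a 14 v 7 day contrast arises only if the Alternate Scenario applies and Arm B is carried forward.

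**The case against.** A reader might infer that the duration question gets no answer in this trial. The documents do not support that. Part 1 reports an odds ratio against E for every active arm, from which point estimates of B v A and C v D follow by division. It also reports each arm's percentage with an interval. Selection is framed against an external doxycycline benchmark and all available data, not as a test between durations, and whether an arm reaches a benchmark can be judged from that arm alone. Part 2 then plans active-v-active comparisons. No Part 1 objective or hypothesis names a duration contrast; the duration-ranging wording stands in the SAP introduction. All of this stands.

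It is also fair that the highest power, about 84%, is a favourable case: a 20-point gap, with an ICC of 0.01 that the plan assumed for the 90% combination arm and not for Arm B. And a superiority test that fails at 28–48% power cannot justify a shorter course.

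The objection does not remove the gap. A benchmark does not estimate what a shorter regimen loses; the intervals offered for reading arms side by side are too narrow wherever worms cluster within subjects; and Part 2 comes too late to guide its own choice of arms.

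**Conclusion.** The point holds in a limited form. Part 1 plans no direct, clustering-adjusted estimate of either duration effect, although duration is part of its described purpose and of the selection rule. The indirect evidence is usable for point estimates but misleading on precision: about 9 v 16 points of half-width at 70% with ICC 0.54, and almost no difference where ICC is 0.01.

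A reader might also infer that adding the contrasts would settle which duration to take forward. It would not. Power is about 70–84% for 90% v 70% and about 28–62% for a 10-point gap, so the value lies in the interval and not in the p-value. These figures rest on assumed rates, 25 evaluable subjects per arm, the plan's worm-count distribution and ICCs between 0.01 and 0.54, and a GEE stand-in for the planned model. The primary tests are unaffected.

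**What to change.** In SAP 9.3.2, and in protocol 10.5, add B v A and C v D as prespecified exploratory odds ratios with confidence intervals from the same five-arm alternating logistic regression, labelled as supporting regimen selection. To count as prespecified, they must be added before Part 1 is unblinded. State beside them that a non-significant result is not evidence of equal efficacy, and give the power range above as the reason.

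Extending the two pairs to the SAP 9.4.2 secondary endpoints is optional and should be descriptive. It would also help to give per-arm intervals that allow for clustering, or to note that the Wilson intervals do not.

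The cost is two contrast statements and a few lines of text, with no new subjects or data. The downside is two more unadjusted exploratory estimates in a set that the plan already leaves unadjusted.

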In order also to assess the effect of a dose of ivermectin at Month 6, participants will be randomised into four treatment arms, with the best candidate based on Part 1 results administered with ivermectin and with ivermectin placebo at Month 6.

Within each treatment arm, subjects will be stratified by the number of operable sites with onchocercomata and by mean screening skin mf. There will be four strata, i.e. 1 site and less than or equal to 5 mf/mg, more than 1 site and less than or equal to 5 mf/mg, 1 site and more than 5 mf/mg, more than 1 site and more than 5 mf/mg.

A total of either 294 subjects (Base Scenario) or 336 subjects (Alternative Scenario) will be recruited. The Base Scenario will be employed:

- if neither Arm C nor Arm D from Part 1 is selected for continued enrolment in Part 2, or
- if either Arm C and/or Arm D in Part 1 is selected for continued enrolment in Part 2 and Arm C and/or Arm D has demonstrated superiority over both Arm E and Arm A in Part 1.

[figure not shown]
The Alternative Scenario will be employed if either Arm C and/or Arm D in Part 1 is selected for continued enrolment in Part 2, but Arm C or Arm D in Part 1 has not demonstrated statistical superiority over both Arm E and Arm A.

In the Base Scenario, subjects will be randomised continuously 2:2:2:1 into one of four parallel treatment arms until group size is achieved:

- Arm K (n = 84): initial treatment with an active regimen selected from Part 1, followed by ivermectin at Month 6;
- Arm L (n = 84): initial treatment with the same active regimen selected from Part 1 as Arm K, followed by ivermectin matching placebo at Month 6;
- Arm M (n = 84): initial treatment with a second active regimen selected from Part 1, followed by either ivermectin or ivermectin matching placebo at Month 6 (decision to be made prior to Part 2);
- Arm N1 (n = 42): initial treatment with ABBV-4083 matching placebo and albendazole matching placebo, followed by ivermectin at Month 6.

Details of timing and sequence of investigations and measures are provided in the Schedule of Events (see Appendix 2). The overall design for Part 2 Base Scenario is presented in Figure 2.

Figure 2. Overall Design for Part 2 - Base Scenario

4083 = ABBV-4083; Alb = albendazole; d = days; D = (study) day; IVM = ivermectin; M = month; Pbo = placebo

In the Alternate Scenario, subjects will be randomised continuously 1:1:1:1 into one of four parallel treatment arms until group size is achieved:

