10.1 Statistical Hypotheses

10.1.1 Primary Hypothesis in Part 1

The primary hypothesis for the proof of concept in Part 1 is that more worms will have *Wolbachia* depletion at 6 months in the subjects who completed treatment with ABBV-4083 for 7 days (Arm A), ABBV-4083 for 14 days (Arm B), ABBV-4083 + albendazole for 7 days (Arm C), or ABBV-4083 for 7 days + albendazole for 3 days (Arm D) than in subjects treated

with albendazole for 7 days (Arm E) among all subjects who completed treatment and who had live female worms from nodulectomies at 6 months.

The primary hypothesis to satisfy the combination rule in Part 1 is that more worms will have *Wolbachia* depletion at 6 months in the subjects treated with ABBV-4083 + albendazole for 7 days (Arm C) than in subjects treated with albendazole for 7 days (Arm E) or those treated with ABBV-4083 for 7 days (Arm A) among all subjects who completed treatment and had live female worms from nodulectomies at 6 months. If the combination arm of ABBV-4083 for 7 days + albendazole for 3 days (Arm D) is to advance to Part 2 and ABBV-4038 for 7 days + albendazole for 7 days (Arm C) is not, then the combination rule will be tested for ABBV-4083 for 7 days + albendazole for 3 days (Arm D) in Part 1. Of note, the possible substitution of ABBV-4083 for 7 days plus albendazole for 3 days in place of ABBV-4038 + albendazole for 7 days will not be continuously noted below for brevity sake.

10.1.2 Primary Hypotheses in Part 2

The primary hypothesis for Part 2 is that more subjects treated with one or more of the active regimens selected from Part 1 (Arms K, L and M) will be without skin microfilariae at 24 months as compared to subjects treated with placebo (Arm N1, base scenario) or ABBV-4083 for 7 days (Arm N2, alternate scenario).

Combination Rule Hypothesis for Part 2 Alternative Scenario

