10.5 Population Level Summary and Analysis for the Primary Endpoints

The Part 1 primary and combination endpoints, the proportion of adult female worms without *Wolbachia* endobacteria assessed by immunohistology at 6 months, will be summarised among

the PP for ND6M population, and the odds ratio for each of the treatment arm comparisons of interest (Arm A vs E and Arm B vs E; Arm C vs E, Arm C vs A; Arm D vs E, Arm D vs A) will be calculated using contrasts within an alternating logistic regression model with treatment arm as factor and also accounting for within-subject correlation, each at 2-sided $\alpha = 0.10$.

The Part 2 primary endpoint of the percentage of subjects without skin microfilariae at Month 24 will be summarised across the PP for microfilariae population, and the adjusted odds ratio for each of the 3 active treatment arms will be compared to the comparator arm (Arm K vs N1 or N2, Arm L vs N1 or N2, and Arm M vs N1 or N2) using contrasts within a logistic regression model with treatment arm as factor and number of sites per subject (1, > 1) and mean baseline mf $(\le 5, > 5)$ as covariates at 2-sided $\alpha = 0.017$. Supportive subgroup analyses for the primary endpoint will also be performed for at least the following subgroups: number of sites per subject (1, > 1) and mean baseline mf $(\le 5, > 5)$.

The Part 2 combination rule endpoint for the alternate scenario, the proportion of adult female worms without *Wolbachia* endobacteria assessed by immunohistology at 6 months across all subjects treated with the same regimens in Parts 1 and 2 will be summarised among the PP for ND6M population, and the odds ratio for the comparison of interest (Arm K plus Arm L vs N2 [or Arm M vs Arm N2 if ABBV-4083 for 14 days is chosen for Arms K and L]) will be calculated using contrasts within an alternating logistic regression model with treatment arm as factor. P-values for the odds ratio of Part 1 and Part 2 will be combined using an inverse normal combination test and tested at 2-sided $\alpha = 0.10$.

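### If Arms C and D both advance, the SAP omits D v A although protocol 10.5 and 10.7 list it, and protocol 3.3 does not say clearly which Part 2 scenario follows

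*SAP*

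**What the plan says.** SAP 9.3.2 gives two lists of contrasts.

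- The first is unconditional: "For proof of concept: (1) A vs. E, (2) B vs. E, (3) C vs. E, (4) D vs. E".
- The second serves the combination rule. If C advances, it is C v A and C v E. For Arm D, it is "if Arm D is to advance to Part 2 but Arm C is not, then: (1) D vs. A, (2) D vs. E".

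SAP 2.1 and the estimand table (Table 1) treat D in the same way, as a stand-in for C.

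The protocol is divided. Section 10.1.1 agrees with the SAP: when D advances and C does not, "then the combination rule will be tested for ABBV-4083 for 7 days + albendazole for 3 days (Arm D) in Part 1". Section 10.5 attaches no condition to its list, which includes "Arm C vs E, Arm C vs A; Arm D vs E, Arm D vs A". Section 10.7 also names "Arm D vs Arm A and Arm D vs Arm E" among the primary-endpoint comparisons, each at 2-sided 0.10 with no multiplicity adjustment. The synopsis repeats the unconditional list.

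SAP 1.0 states: "All analyses in this SAP are consistent with what is described in the study protocol unless otherwise noted in Section 13.0". Section 13.0 has no entry on this point.

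Protocol 3.3 allows up to two regimens to advance and uses the result to choose the Part 2 design. Where C and/or D is selected, the Base Scenario applies if "Arm C and/or Arm D has demonstrated superiority over both Arm E and Arm A in Part 1". The Alternative Scenario applies if C *or* D has not shown that superiority.

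**The concern.** The combination rule asks whether the combination beats each drug alone. For D, the part of that question which concerns albendazole's contribution is D v A, since both arms receive ABBV-4083 for 7 days. D v E cannot answer it, because E contains no ABBV-4083. C v A cannot answer it either, because C has 7 days of albendazole and D has 3.

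The result also has a use. Protocol 3.3 takes the C and D contrasts with A and E to choose between a placebo comparator (Arm N1, 294 subjects) and an ABBV-4083 comparator (Arm N2, 336 subjects). If both arms advance and the SAP is followed as written, one input to that choice is missing. The regimens are chosen from unblinded Part 1 data (protocol 10.9), so whether D v A is formally tested would follow from a choice made with the results in hand.

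**Working it through.** **1. Which contrasts are needed and which the SAP supplies**

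| Advancing combination arms | Contrasts that protocol 3.3 refers to | Supplied by SAP 9.3.2 |
|---|---|---|
| Neither | none (Base Scenario) | – |
| C only | C v A, C v E | both |
| D only | D v A, D v E | both |
| C and D | C v A, C v E, D v A, D v E | all except D v A |

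The gap is confined to the last row and to one contrast. D v E is always run as proof of concept.

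**2. What 3.3 says in that row**

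Suppose C passes and D is untested, or is tested and fails. The *and/or* in the Base definition is met through C. The *or* in the Alternative definition is met through D. Both readings are open, so supplying D v A alone does not settle the scenario. The pooled Part 1 and Part 2 test in protocol 10.1.2 does not help, because it uses D only when C is not selected.

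**3. The plan's own power figure**

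Inputs (protocol 10.3.1, SAP 2.4): 25 evaluable subjects per arm, 90% v 70% of worms without *Wolbachia*, 2-sided α = 0.10, ICC 0.01 in the 90% arm and 0.54 in the 70% arm, and the stated distribution of 1 to 10 worms per subject (mean 3.79).

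Approximate effective worms per subject = Σ P(n)·n / [1 + ICC(n − 1)].

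- ICC 0.54: 1.406, so 25 × 1.406 = 35.2 per arm.
- ICC 0.01: 90.9 per arm of 25.

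Logit difference: 2.197 − 0.847 = 1.350. SE = √[1/(90.9 × 0.09) + 1/(35.2 × 0.21)] = 0.508. z = 2.66. Power = Φ(2.66 − 1.645) ≈ 84%.

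Simulation with a marginal logistic model, exchangeable within-subject association and robust standard errors gives 82.0% with a common pairwise odds ratio and 83.7% with arm-specific association, as SAP 9.3.2 specifies. The stated 81% is reproduced closely. SAP 2.4 applies it to Arm C or D, so it also covers D v A.

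**4. D v A at other true rates (assumptions; the documents give no D-specific rate)**

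D at 80%, A at 70%: logit difference 1.386 − 0.847 = 0.539.

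- ICC 0.54 in D: SE = √[1/(35.2 × 0.16) + 1/(35.2 × 0.21)] = 0.559; z = 0.96; power ≈ 25%.
- ICC 0.01 in D: SE = √[1/(90.9 × 0.16) + 1/(35.2 × 0.21)] = 0.452; z = 1.19; power ≈ 33%.

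Simulation gives 27–30% for ICC 0.54 to 0.3. The documents state an ICC at 70% and at 90% but not at 80%, hence the range. At 90% with ICC 0.54 instead of 0.01, simulated power is about 71%.

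**5. Joint behaviour of C v A and D v A (simulated; the contrasts with E are not included)**

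| True C / D / A | C passes | D passes | Both | At least one |
|---|---|---|---|---|
| 90 / 90 / 70% | 83.5% | 83.7% | 76.1% | 91.0% |
| 90 / 70 / 70% | 83.2% | 5.8% | 5.8% | 83.3% |
| 70 / 70 / 70% | 6.1% | 5.8% | 1.5% | 10.4% |

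In the second row C passes and D fails in 77.4% of trials, so D fails in 77.4 / 83.2 = 93% of the trials in which C passes.

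**The case against.** The condition may be deliberate. Protocol 2.4.1 and 3.1 frame the rule as superiority over each agent alone *of equal duration*. C matches both A and E at 7 days, whereas no arm gives albendazole alone for 3 days. Protocol 4.1 ties the Part 2 objective to the 7-day combination, and 10.1.1 calls D a possible substitute. This has some force for D v E. It has less for D v A, where ABBV-4083 is given for 7 days in both arms. Protocol 3.3 also names D in its own right, and the SAP requires D v A whenever D advances alone.

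A second objection is that the SAP has not simply departed from the protocol. That stands: it follows 10.1.1, and the protocol disagrees with itself. A reader might infer an undeclared SAP deviation. The fairer description is an unreconciled conflict that Section 13.0 should have addressed.

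Third, D's results would not be hidden. SAP 9.3.2 reports worm percentages with 95% intervals for every arm, and selection uses efficacy, safety and feasibility together. A success for C over A would also be evidence that albendazole contributes, though not at 3 days. Nor is the condition strictly circular: the choice of arms depends on the data, but the test does not decide its own condition.

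**Conclusion.** The point holds as a conflict between passages with one practical gap. If C and D both advance, the SAP leaves out D v A, which protocol 10.5 and 10.7 plan and which the decision in 3.3 draws on; 3.3 is itself ambiguous in that case.

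A reader might go further and infer that D could enter Part 2 with no test at all. The documents do not support that. The protocol plans D v A, D v E is always tested, and under the Alternative Scenario each active arm is compared with 7 days of ABBV-4083 on Month 24 skin microfilariae. Nor do they say that an arm which misses the rule is barred from Part 2; the Alternative Scenario exists for that case.

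The size rests on assumptions about D's true rate and ICC. The omission matters most if D adds nothing to A: D would then fail in about 93% of the trials in which C passes, and the SAP would not show it. At 80% v 70%, power is about 25–33%, so a failure would say little. At the planned 90% v 70%, the stated 81% applies.

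**What to change.** 1. In SAP 9.3.2 and 2.1 (and Table 1), list D v A unconditionally at 2-sided 0.10, as protocol 10.5 and 10.7 already do.
2. Align protocol 10.1.1 and 10.1.2 with 10.5 and 10.7, including the role of D in the pooled test when C is also selected. Record the change in SAP Section 13.0.
3. Reconcile the two scenario definitions in protocol 3.3. They should say how each advancing combination arm's own contrasts with A and E determine the scenario when C and D both advance and only one meets the rule.

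The first two steps cost wording: the five-arm model already yields the contrast, no Part 1 subjects are added, and the policy of no Part 1 adjustment is unchanged. If neither combination adds to A, the chance that at least one passes rises from about 6% to about 10%.

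The third step can cost more. If 3.3 is settled so that both arms must pass for the Base Scenario, passing on the contrasts with A falls from about 83% (C alone) to about 76% (both) even when C and D are truly at 90%, and further if D is weaker. The Alternative Scenario would then be triggered more often, at 336 − 294 = 42 more subjects and with Month 6 nodulectomies in a subset. That trade-off should be decided and written down before Part 1 is unblinded.
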